3.0 CLINICAL INVESTIGATION DESIGN

This study is a prospective, multi-center, open-label, post-market study designed to evaluate the effectiveness of Abbott neurostimulation devices in restoring pain relief for patients who no longer receive adequate therapeutic benefit from SCS. The Investigator will select the most appropriate BurstDR or DRG implementation method according to their standard of care.

A trial of BurstDR or DRG may be performed as deemed appropriate by the Investigator. This includes the option for multiple trials to test both BurstDR and DRG therapy. Similarly, the permanent implementation method will be performed as deemed appropriate by the Investigator.

This clinical investigation will enroll up to 100 patients at up to 40 sites in the US. Subject enrollment is expected to be completed within 12 months; subjects will be followed for 24 months after permanent implementation.

The clinical investigation has been designed to involve as little pain, discomfort, fear, and any other foreseeable risk as possible for subjects. Refer to the Risks Analysis section of this investigation plan for details.

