5.4 Subject Enrollment

A patient is considered enrolled in the clinical investigation from the moment the patient provides written informed consent and has been confirmed to meet all eligibility criteria.

Any subject enrolled into the clinical investigation who is later found not to meet all eligibility criteria, will be evaluated by the study team. If the deviation is found to violate the scientific integrity of the study or unduly influence the study aims, the subject will be withdrawn from the study. Otherwise, the subject will continue in the study and be included in the analysis population.

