5.6 Subject Withdrawal

Each enrolled subject shall remain in the clinical investigation until completion of the required follow-up period; however, a subject's participation in any clinical investigation is voluntary and the subject has the right to withdraw at any time without penalty or loss of benefit. Conceivable reasons for discontinuation may include, but not be limited to, the following:

- Subject death
- Subject voluntary withdrawal
- Subject lost-to follow-up as described below
- Subject's follow-up is terminated (per Section 3.3)
- Subject's neurostimulation system has been explanted

The Sponsor must be notified of the reason(s) for subject discontinuation. The site will provide this information to the Sponsor. Investigators must also report this to their respective IRB/EC as defined by their institution's procedure(s).

No additional follow–up will be required or data recorded from subjects once withdrawn from the clinical investigation, except for the status (deceased/alive).

However, if a subject withdraws from the investigation due to problems related to the safety or performance of the device under investigation, the Investigator shall ask for the subject's permission to follow his/her status/condition outside of the clinical investigation.

In case of subject withdrawal of consent, the site should make attempts to schedule the subject for a final clinical investigation visit.

Lost-to-Follow-up

If the subject misses two consecutive scheduled follow-up time points, and the attempts at contacting the subject detailed below are unsuccessful, then the subject is considered lost-to-follow-up. Site personnel shall make all reasonable efforts to locate and communicate with the subject (and document these efforts in the source documents), including the following, at each contact time point:

- A minimum of two telephone calls on different days over the specified follow-up windows to contact the subject should be recorded in the source documentation, including date, time and initials of site personnel trying to make contact.
- If these attempts are unsuccessful, a letter (certified if applicable) should be sent to the subject.
- If a subject misses one or more non-consecutive follow-up contact time points, it will be considered a missed visit. The subject may then return for subsequent visits. If the subject misses

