7.3 Adverse Event and Device Deficiency/Device Malfunction Reporting

7.3.1 Adverse Event Reporting

Safety surveillance and reporting starts as soon as the patient is enrolled in the clinical investigation. Safety surveillance and reporting will continue until the last follow-up visit has been performed, the subject is deceased, the subject concludes participation in the clinical investigation, or the subject withdraws from the clinical investigation. All adverse event data, including deaths and device deficiency data (if applicable), will be collected throughout the time period defined above and will be reported to the Sponsor on a CRF. Additional information with regard to an adverse event should be updated within the appropriate CRF.

Unchanged, chronic, non-worsening, or pre-existing conditions are not AEs and should not be reported.

An offline form will be made available to allow the Investigator to report SAEs in the event the entry cannot be made in the EDC. This does not replace the EDC reporting system. All information must still be entered in the EDC system as soon as feasible.

SAE Reporting

The Investigator should report all SAEs to the Sponsor as soon as possible but no later than outlined below.

Clinical Site	Reporting timelines
All Sites	SAEs must be reported to the Sponsor no later than 3 calendar days from the day the site personnel became aware of the event or as per the investigative site's local requirements, if the requirement is more stringent than those outlined.

The date the site staff became aware the event met the criteria of an SAE must be recorded in the source document. The Investigator will further report the SAE to the local IRB/EC according to the institution's IRB/EC reporting requirements.

Reportable events to sponsor are considered:

- 1. All serious adverse events regardless of relatedness to the device and/or procedure
- 2. All device/procedure related adverse events

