3.2 Adverse Events

All adverse events related or unrelated to the device, serious and non-serious will be summarized for all subjects in the Full Analysis Set using the number of events, the number of subjects with event(s), and the percentage of subjects with event(s). All CEC adjudicated adverse events will also be summarized for all subjects in the Full Analysis Set with the number of events, the number of subjects with event(s), and the percentage of subjects with events.

3.3 **Subject Early Termination**

Subject early termination reasons including deaths, withdrawals, lost-to-follow-up, etc. will be summarized for subjects in the Full Analysis Set. A listing will also be provided for subjects who deregistered from the study with reasons for de-registration.

3.4 **Protocol Deviation**

Protocol deviations will be summarized descriptively by category for subjects in the Full Analysis Set in whom a protocol deviation was reported.

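### SAP 3.2 reports adverse events only as counts and crude percentages of the Full Analysis Set, with no phase and no time at risk, so the percentages estimate no defined risk

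*SAP*

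**What the plan says.** SAP 3.2 contains two summaries. The first is broad: "All adverse events related or unrelated to the device, serious and non-serious will be summarized for all subjects in the Full Analysis Set", expressed "using the number of events, the number of subjects with event(s), and the percentage of subjects with event(s". The second uses the same measures: "All CEC adjudicated adverse events will also be summarized for all subjects in the Full Analysis Set". SAP 2.2.2 adds only counts, percentages or rates, and optional exact intervals. Neither section defines a start date, a phase, person-time or a time-to-event method.

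The observation window comes from the protocol. Section 7.3.1 opens it early: "Safety surveillance and reporting starts as soon as the patient is enrolled in the clinical investigation". Under section 5.4, "A patient is considered enrolled in the clinical investigation from the moment the patient provides written informed consent" and eligibility has been confirmed, which is before baseline, any trial period and implementation. Section 7.3.1 also sets the end: "Safety surveillance and reporting will continue until the last follow-up visit has been performed", or until death, conclusion of participation or withdrawal if one of these comes first. The follow-up clock starts elsewhere. Section 3.0 says "subjects will be followed for 24 months after permanent implementation".

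Section 5.6 lists explant among the reasons for discontinuation and says "No additional follow–up will be required or data recorded from subjects once withdrawn from the clinical investigation", apart from vital status. It also provides for an attempted final visit when consent is withdrawn. A subject who leaves over device safety or performance is to be asked for permission to be followed outside the study. SAP 3.3 tabulates reasons for early termination but does not connect them to adverse-event exposure.

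**The concern.** A percentage of subjects with an event describes a risk only if the period of observation is stated and is about the same for everyone. Here neither is so. The window opens before the study device is in place, by an interval that varies between subjects, and it closes at individual exit. A subject who leaves at month 3 without an event carries the same weight in the denominator as one observed for 24 months. A serious event on the old system while the subject waits for a trial or implant falls in the same summary as one after implantation.

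These percentages are what a clinician will read as the safety result of replacing a failed system. As specified, they are neither a per-procedure risk nor a risk over a stated time after implantation, and they cannot be compared with another study that had different attrition or waiting times.

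**Working it through.** The plan gives no adverse-event rate, exit rate or precision target, so it has no figure to reproduce. All rates below are assumptions.

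**1. Windows side by side**
- Numerator: events from enrolment to own exit (Protocol 7.3.1).
- Denominator: the whole Full Analysis Set (SAP 3.2).
- Follow-up clock: 24 months from permanent implementation (Protocol 3.0).
- Data after exit: vital status only (Protocol 5.6).

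**2. Effect of early exit on events after permanent implementation**

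Assume a true 24-month risk R = 0.20, a constant event rate, a share e leaving evenly over the 24 months, and exit unrelated to events.
- Cumulative rate: L = −ln(1 − 0.20) = 0.2231.
- Mean risk observed in those who leave: 1 − R/L = 1 − 0.20/0.2231 = 0.1037.
- Crude proportion: (1 − e) × 0.20 + e × 0.1037.

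Now let half of the risk fall at implantation. The remaining risk is 0.10/0.90 = 0.1111, with L = 0.1178. The mean in those who leave is 1 − 0.1111/0.1178 = 0.0566 (unrounded L). The crude proportion is 0.10 + 0.90 × [(1 − e) × 0.1111 + e × 0.0566].

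| Share leaving early | Constant rate | Half of the risk at implantation |
|---|---|---|
| 10% | 19.0% | 19.5% |
| 20% | 18.1% | 19.0% |
| 30% | 17.1% | 18.5% |
| 40% | 16.1% | 18.0% |

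As a check, exponential instead of uniform exits with a constant event rate give 18.0%, 16.9% and 15.8% at 20%, 30% and 40%. If all exits fell at month 3, the 20% case would read 16.6%.

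**3. Effect of pre-device events**

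Let p be the probability of a countable event between enrolment and first study device. The all-phase percentage is 1 − (1 − p)(1 − crude). Take the 20% exit case, crude 0.1807:
- p = 2%: 1 − 0.98 × 0.8193 = 19.7%, just below 20%.
- p = 5%: 1 − 0.95 × 0.8193 = 22.2%, above 20%.

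The sign of the net error depends on p and e, and the documents give neither.

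**4. Effect of the denominator**

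Protocol 5.5 removes from the Full Analysis Set subjects to whom no study device was introduced. If a trial system counts as a study device, a subject who had a trial but no permanent system stays in the denominator with no time at risk in the permanent phase. If such subjects were 10% or 20% of the set (assumption), a 20% permanent-phase risk would read 0.90 × 20% = 18% or 0.80 × 20% = 16%.

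**The case against.** Several arguments against the point have force.

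- **Mixing is limited.** Protocol 7.3.1 lists as reportable all serious events and all device- or procedure-related events. The visit lists in Protocol 6 record device-related and serious events from trial implementation onward, and the baseline list records none. Relatedness is judged event by event. What gets mixed in before the device is therefore mainly unrelated serious events. The CEC adjudicates serious device- or procedure-related events (Protocol 3.2), so its summary should largely exclude them. The SAP wording may also mean separate rows by relatedness and seriousness. This stands, and it confines the mixing to the all-event and serious-event figures.
- **Direction.** A reader might infer that the plan understates risk in the device's favour. The documents do not support that for all events, because pre-device events push the figure up. Nor does the SAP call its percentage a 24-month risk.
- **Explant.** Once a system is removed, device exposure has ended. For that kind of exit the crude proportion is itself a valid cumulative incidence. Explant for infection or another complication usually follows an event that has already been counted. A reader might reach for Kaplan-Meier with explant censored, but that could overstate device-exposed risk. For the same reason the explant proportions in Protocol 1.1.1 (9.2% to 23.9%) do not supply the exit rate used above. They are also retrospective, with no 24-month horizon given for them.
- **Size.** With 100 subjects, an exact 95% interval around 20% runs from about 12.7% to 29.2%, wider than any shortfall in the table. This is a fair limit on importance. It does not remove a systematic error that is cheap to avoid.
- **Unseen material.** The table mockups and the text of SAP 2.1.1 are not available, so a phase split there cannot be excluded.
- **Role of safety.** Adverse events are descriptive in this single-arm study and are not a listed endpoint, and SAP 3.3 will show attrition. That argues for a modest priority.

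**Conclusion.** The point holds in limited form. SAP 3.2 specifies two crude summaries with no phase and no time at risk, over a window that starts before the device and ends at individual exit. For all events and serious events the two distortions run in opposite directions and the net sign is unknown. That is a reason to separate them, since nothing shows that they cancel.

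For device- or procedure-related events after permanent implementation, the crude percentage falls below the 24-month risk to the extent that subjects withdraw or are lost for reasons unrelated to events. At a true risk of 20% the shortfall is about 1.9, 2.9 or 3.9 points for exits of 20%, 30% or 40%, assuming a constant rate and evenly spread exits. It is about half that or slightly more (1.0, 1.5 or 2.0 points) if half of the risk falls at implantation, and smaller again with fewer exits. The change is worth making because it costs little. No main conclusion of the study depends on it.

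**What to change.** In SAP 3.2:

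1. State the adverse-event window and tabulate events by phase: enrolment to first study device, each trial period, and permanent implementation to exit. Use as denominator the subjects who entered that phase.
2. For device- or procedure-related events and for serious events after permanent implementation, add events per subject-year and a cumulative incidence at 6, 12 and 24 months with 95% confidence intervals. Use the cumulative incidence function, with death and explant as competing events and other exits censored.
3. Keep the planned counts and crude percentages alongside, for both the all-event and the CEC-adjudicated summaries.

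The protocol already records events at trial implementation, end of trial, permanent implementation and each follow-up visit, so no new visits should be needed. The cost is a few extra descriptive tables, and the stated post-implementation risks may come out slightly higher.

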3.5 Additional Data

For PCS Total score, change from baseline to 6 months will be reported for subjects in Full Analysis Set, who are catastrophizing at baseline (PCS Total score at baseline >=30).

4.0 DOCUMENTATION AND OHER CONSIDERATIONS

4.1 Changes from Protocol Specified Analysis

Additional hypothesis testing is added in section 2.3.1 per study team's decision.

4.2 Analysis Software

All analyses will be performed using SAS® for Windows, version 9.2 or higher.

